STUDY PROTOCOL [VG-Social ABCs]

Parent-mediated intervention for toddlers with early social communication challenges or emerging autism: A multi-site randomized controlled trial of a group-based virtual program that empowers parents as change agents

1. The Need for a Trial

Autism spectrum disorder (hereafter ASD or autism) is a neurodevelopmental disorder with increasing prevalence (>1.5%)¹ and high personal, familial, and societal burdens. Core ASD symptoms include deficits in social communication and interaction (including impaired social-emotional reciprocity and difficulty developing social relationships), and repetitive/restricted patterns of behaviour and/or interests². Many autistic individuals require substantial and costly care across the lifespan from developmental, educational and behavioural services³, as well as health and mental health sectors⁴ due to high rates of comorbid conditions such as anxiety, depression, and ADHD⁵⁻¹⁰. Parental mental health is also often negatively affected, with elevated levels of stress¹¹, anxiety, depression, and burnout¹². Access to early intervention can reduce long-term costs³, but is severely hampered across Canada by long wait times for diagnosis and entry to intervention services. Developing innovative solutions that increase access to earlier intervention and parental supports can mitigate the need for intensive developmental services and later supports, thus reducing down-stream individual, family, and system costs and improving long-term outcomes^{3,13}.

1.1 What is the problem to be addressed?

Across Canada, toddlers with autism have almost no access to diagnosis-specific intervention due to years-long delays in accessing a diagnosis (i.e., up to two years)^{14,15} followed by at least an additional two years' wait to access intervention services in many areas¹⁶. These delays have only been exacerbated by Covid-19-related isolation measures¹⁷. This means that the vast majority of high-risk toddlers miss out on early intervention during the narrow developmental window when their brains are most amenable to treatment. Concurrently, parents of children with autism, already at risk for significant mental health challenges^{11,12}, experience increasing distress as they watch their children fail to achieve key developmental milestones and as they struggle to manage their toddlers' emotional dysregulation associated with core autism symptoms and functional communication deficits. Long-term cascading effects result in children requiring more intensive and/or longer duration of later interventions, with increased costs to the system, coupled with parental hopelessness leading to burnout¹². This dire situation can be mitigated by capitalizing on ***parent-mediated intervention*** that takes place in the family's home and can be initiated at the first signs of risk for autism (i.e., as early as one year of age¹⁸). ***Empowering parents to become engaged as the active agents of change for their toddlers, as early as possible, can significantly enhance child outcomes and mitigate parental stress.***

Informed by two decades of longitudinal research with high-risk infants and toddlers^{19,20}, our team developed and demonstrated the efficacy of a 12-week parent-mediated intervention for toddlers with confirmed or suspected autism (the *Social ABCs*)^{21,22}. Co-created with parents and Coaches, the approach operates within a developmental framework, in the child's natural environment, using strategies of applied behaviour analysis (thus a Naturalistic Developmental Behavioural Intervention; NDBI)²³. By directly targeting the parent-child dyad, the intervention

yields positive outcomes for both toddlers and their parents that are foundational for positive developmental and mental health outcomes: increased positive affect-sharing and social communication in toddlers, and parental empowerment via bolstering their skills and confidence in supporting their children's development (study findings are further detailed below).

1.2 What is the principal research question to be addressed?

In toddlers (aged 18–42 months) with confirmed or suspected autism, is virtual, Group-based intervention using the *Social ABCs* model, more effective than treatment as usual at increasing toddlers' vocal responsiveness to their primary caregivers (i.e., parents)?

1.3 Why is a trial needed now?

Given the rapidly rising prevalence of autism, and significant barriers to accessing traditional interventions, there is an urgent need to develop and evaluate innovative delivery models that can be accessed when the first signs of autism emerge. Promising ways to address this urgent need include (1) involving primary caregivers (hereafter, 'parents') as mediators of the intervention, (2) increasing access via virtual platforms, and (3) providing group-based interventions.

Recent reviews highlight the promise of ***parent-mediated interventions*** for young children with emerging autism, with evidence of gains in key areas of social, communication, and play development^{23,24}. A small number of studies have also examined the efficacy of ***virtual parent training methods***, motivated by efforts to increase access. A recent systematic review²⁵ identified 7 studies of virtual parent-training models, three of which focused on toddlers with autism. Limitations due to weak study design (only 2 studies were RCTs), small samples, lack of measurement of child outcomes, no blinding, and variable or unspecified treatment durations were identified. Only three studies used live, two-way videoconferencing, and only one of these involved toddlers²⁶, but with a very small sample ($n = 8$). Despite these limitations, the review concludes that virtual training in parent-mediated intervention "could benefit both parents and children with ASD given the barriers they face in accessing traditional services"²⁵.

A very recent review of virtual delivery ("video-therapy") in general mental health intervention identifies the rapid increase in virtual intervention in response to Covid-19 isolation measures, highlighting the need for more evidence in support of such approaches²⁷. With respect to ***group-based*** video-therapy, the authors conclude that the evidence is even more scant, but extant literature does point to feasibility and "roughly comparable outcomes between in-person and tele-group treatments"²⁷. Group-based mental health approaches stand apart as being more cost-efficient than individual therapy, and having potential to add unique therapeutic value²⁸.

Supported by the above evidence, we argue that an innovative and promising approach to increasing access to autism intervention in the very early years involves virtual delivery of a group-based approach to parent training. We are currently pilot testing such an intervention (described below), which is now ready for formal evaluation through a well-powered RCT.

The *Social ABCs* intervention is uniquely well-poised for virtual delivery as evidenced by the initial success of our pilot evaluation (see below). Our model differs substantially from many approaches in its use of a specific set of manualized, active, in-the-moment, supportive parent-coaching strategies that are easily translated to virtual delivery. For example, although used by almost all other parent-mediated approaches, we intentionally *avoid* a training technique called

‘modelling’ (i.e., working directly with the child to demonstrate strategies to the parent). Our intentional avoidance of modelling was motivated by a commitment to supporting parents to develop their own ‘style’, to promote positive parent-child interaction, and foster parental empowerment. This unique coaching stance, shown in our previous work to successfully promote parent skill acquisition and self-efficacy, makes the *Social ABCs* ideally suited to virtual delivery. The ***virtually delivered Group-based model***, proposed for the current evaluation, is an adaptation of our original (12-week, individual, in-person) *Social ABCs* program. Our original model has been shown to be feasible and acceptable²¹, and a cross-site RCT²² demonstrated improvements in toddlers’ communication skills (i.e., significant gains in toddler vocal responsiveness and initiations; $p < .001$), parent positive emotion-sharing ($p = .017$; which predicted gains in child smiling), and a trend toward increased toddler social orienting ($p = .054$). Parents learned the techniques (i.e., fidelity >80%) and reported increased self-efficacy ($p = .009$)²²; qualitative analyses of parent interviews revealed themes of empowerment and hopefulness²⁹. We have also now successfully completed a large community implementation ($n = 183$)³⁰⁻³³, with effectiveness commensurate with efficacy shown in our initial RCT, across a wide range of parent factors (gender, English language learner status, educational attainment [ranging from grade 9 to graduate school completion]) and child variables (age, sex, language skills)³². We have made two key adaptations to the original model, with promising pilot findings (described in section 2.19).

1.4 How will the results of this trial be used?

This project addresses the acute developmental and mental health needs of individuals with disabilities, as well as their families, identified by KBHN and CIHR as priority populations. Outcomes will establish the evidence needed to fill an urgent gap in the system –increasing access to treatment for toddlers at the first signs of risk by empowering parents as the agents of change.

In most Canadian jurisdictions, ASD service funding is very difficult to access under age two. Moreover, there is a complete lack of funding/services specific to the needs of toddlers with emerging signs of ASD who do not yet have a confirmed diagnosis. There is a traditional care pathway of generic followed by diagnosis-specific intervention that misses opportunities for more targeted approaches. Similarly, there is a chronic gap, in publicly funded community service models, between early detection and early intervention that does not reflect the state of current evidence (i.e., we can identify the early signs, but despite the existence of evidence-based interventions, there is little that parents can access when initial signs are identified).

Results from this trial will contribute evidence that can be used to make the case for very early intervention as soon as autism-related concerns arise. Exploratory examination of factors related to feasibility and acceptability will inform future implementation work. Our research is embedded in community-based clinical intervention programs, with training partnerships across Canada (e.g., McMaster Children’s Hospital, Children’s Hospital of Eastern Ontario, and Glenrose Rehab Speech-Language services in Alberta) and ongoing collaborations in India (Sethu Centre for Child Development in Goa, as part of the Indo-Canadian Autism Network Symposium; see www.socialabcs.ca for details) and in Israel (in collaboration with The Hebrew University; see www.autismchildfamily.com for details).

Knowledge mobilization will involve engaging Holland Bloorview's Evidence-to-Care team to co-develop lay summaries, and support uptake of research findings into practice. We will share study findings through scientific conferences and community meetings (e.g., Infant Mental Health Promotion, Canadian Paediatric Society (CPS), infant development, psychiatry and psychology training programs, and relevant provincial ministries). Team members' leadership roles within professional associations and relevant policy-advisory groups (see CVs and Most Significant Contributions) will provide platforms through which to share findings and influence provincial policy and national practice. Our team has an established record of translating empirical findings into clinical practice (e.g., CPS practice statements, 2019; www.cps.ca/en/documents/tag/autism).

1.5 Are there any risks to the safety of participants involved in the trial?

We have delivered the *Social ABCs* intervention to over 300 families (across our initial pilot study, two RCTs, community implementation work, and our current pilot evaluation of the in-person and virtual Group models) without any significant adverse events. Use of a virtual platform presents potential risks associated with breach of privacy (mitigated by the use of *Zoom for Healthcare* which is compliant with Canadian healthcare privacy and security regulations). Risk of miscommunication or of missing out on important indicators of mental distress may also be elevated. However, “seeing” more of the family/home circumstances may also provide increased information that would guide the need to follow up regarding mental health or social supports. As with in-person intervention trials, our team is equipped to support parents who express distress (often associated with this early phase of identifying their young child’s developmental challenges) via providing supportive advice, offering families access to local team leads (all with clinical credentials), and/or helping families navigate community mental health resources, as appropriate. Notably, our parent-mediated intervention (which might be viewed as placing extra demands on parents) did *not* lead to increased stress in our original RCT²².

1.6 How will potential participants learn about the study?

The study team will prepare recruitment letters (to be approved by REB) and will share these electronically with community leaders and clinicians both within and outside of the main study centres (Holland Bloorview, Glenrose Rehab, and the IWK). These letters will be sent at the beginning of our recruitment period, and the clinicians receiving the information letters will share them with potential participants at the time of clinical care. This is the same process that we have used for recruitment in our previous and ongoing studies and it has worked very well. Families are given the recruitment letters and they may call our team if interested in participating or learning more.

2. The Current Trial

2.1 What is the trial design?

This is a multi-site, single-blind, randomized group treatment trial. Participants are subjected to three design components (further detailed below): (1) parallel group design with a treatment and an active control arm, (2) own-control (within subject) design for the control arm after these

participants receive treatment (control-treatment), and (3) growth curve analysis of treatment group at *Time 0* (baseline), *Time 1* (after treatment), and *Time 2* (follow-up).

2.2 What are the planned trial interventions?

Once consent is obtained, baseline (*Time 0*) video and questionnaire data are collected and then allocation to treatment arm is revealed. In cases of allocation to Arm A, an assigned Coach meets with each family to discuss family scheduling preferences for coaching sessions, technology issues, and child skills/interests, and then intervention begins.

Arm A. The ***intervention*** is the ***Group Social ABCs, adapted for virtual delivery (VG-Social ABCs)***. The intervention will be provided to small groups of parents (4-8 per group) who meet virtually for a series of six didactic learning sessions led by two Coaches, supported by our **Parent Manual** available in English and French; although all coaching will be in English), PowerPoint slides and involves facilitation discussion, reflection, and idea generation. Each family is assigned a Coach, and one parent per family will receive nine individualized, 1:1 coaching sessions over a 6-week period ***via the virtual platform*** (see Appendix A for study sessions). Parents will participate in an introductory virtual session at which the Coach introduces the aims and structure of the program, discusses family scheduling preferences, technology issues, and child skills/interests, obtains research consent, and collects a ten-minute pre-coaching video recording of the child interacting with the parent (*time 1*); baseline questionnaires are completed at this time as well. Following the 6-week intervention, a second parent-child interaction video is taken (*time 2*) and post-intervention questionnaires are completed by the coached parent; a follow-up video is collected at *time 3* (see below). For all video recordings, parents are instructed to: “*play with your child as you typically play, and try to capture both you and your child on the video*”. Videos will be collected over the virtual platform, saved to virtual drives within institutional firewalls, and shared securely for video coding, based on formal data sharing agreements. Parent Coaches will be existing *Social ABCs* Coaches from all three sites (with backgrounds in Psychology, Early Childhood Education, Speech-Language Pathology, or Applied Behaviour Analysis), all with substantial in-person parent coaching experience, recent virtual coaching experience, and cross-site reliability. Our team will meet regularly to ensure consistency of virtual coaching practices and for supervision, using case-based video review per our longstanding model of cross-site reliability and clinical supervision. During this phase, families will be asked to limit other interventions to 1 hour/week each, as per our current protocols. See Appendix B for contents and selections from Parent Manual and Coaching Manual.

2.5 What are the planned inclusion/exclusion criteria?

Inclusion Criteria. Eligibility will be based on elevated scores on the Autism Parent Screen for Infants (APSI³⁷) supported by expert clinician impression of red flags for autism spectrum disorder (ASD), or a confirmed diagnosis of ASD made by a qualified professional (parents will be asked to provide the clinical report). Toddlers will be between ages 12 and 42 months at enrollment, having been born between 36 and 42 weeks’ gestation, with birthweight $>2,500$ g and no neurological, genetic, or severe sensory or motor conditions. Participating families must be residing in Ontario, Nova Scotia, or Alberta at the time of participation.

Requirements for participation include ability to comprehend verbal English instructions. Our Parent Training Manual is written at a grade four language level, but concepts are shared verbally and through images, so literacy is not a requirement. Participation is also dependent on access to high-speed internet and willingness to be video-recorded, for cross-site consistency checks and data acquisition. Parents will be asked to limit other social communication intervention programs (e.g., through Speech-Language Pathology, Occupational Therapy, Applied Behaviour Analysis, or related services) to 1 hour per week. Parents will also complete weekly services log to document involvement in such programs. Finally, parents will be encouraged to try not to miss more than 2 sessions in a row. Missed sessions will be rescheduled if possible. However, all families will be invited to provide end-of-study data even if multiple sessions are missed (number of sessions attended will be used as a covariate in analyses). Families may withdraw at any time.

There are no ***exclusion criteria*** other than failure to meet inclusion criteria.

2.6 Proposed duration of treatment period.

Treatment duration is 6 weeks. Time span between data collection time points will range from 7 to 9 weeks to allow for re-scheduling if necessary.

2.7 Proposed frequency and duration of follow up.

Data will be collected for both groups at: baseline (*Time 0*), 6 weeks later (*Time 1; within 6-8 weeks*), and following the next 6 weeks (*Time 2; within next 6-8 weeks*). Time 2 for the treatment group provides follow-up data to examine maintenance of gains in our primary outcome (toddler vocal responsiveness) and parent fidelity.

2.8 What are the proposed primary and secondary outcome measures?

Primary Outcome: Toddler vocal responsiveness (blind video-coded).

Secondary Outcomes: 1. *Toddler outcomes:* (a) vocal initiations, (b) social orienting, (c) words understood and used, (d) autism symptoms; 2. *Parent outcomes:* (a) implementation fidelity, (b) self-efficacy, (c) stress.

Exploratory Analyses: 1. *Predictors:* Child factors (e.g., sex assigned at birth, age, baseline language level, ASD symptoms) and parent/family factors that may influence outcomes (e.g., parent gender, parenting role, educational attainment, employment, stress, ethnicity, English spoken at home, family structure)⁴⁰; 2. *Implementation metrics:* Feasibility and acceptability (see below).

2.9 How will the outcome measures be measured at follow up?

Primary Outcome: Toddler vocal responsiveness. Consistent with our previous work^{21,22}, video coding will be used to measure toddlers' vocal responsiveness (proportion of appropriate child vocal responses following a caregiver prompt, from 10-minute video). All video coding will be conducted by blinded research staff with established reliability, per established protocols. *The primary outcome is change in toddler vocal responsiveness from time 0 to time 1.*

***For all parent-child interaction videos**, parents are instructed to: “*play with your child as you typically play*” and reminded that: “*we want to see both of you on the screen as much as possible*”. **Two 10-minute video clips** will be collected and coded per time point (using average per time-point for analyses); **no coaching occurs during data videos**. Videos will be collected by research staff over the virtual platform, saved to virtual drives within institutional firewalls, and shared securely for coding, based on formal data-sharing agreements. **Blinded research staff with established inter-rater reliability will code all videos, per established protocols.**

Secondary Outcomes (all measures used in our previous and/or ongoing work):

1. *Toddlers.* (a) Vocal initiations and (b) social orienting (both blind-coded from video); (c) parent-rated word inventory (MacArthur-Bates Communicative Development Inventory [CDI]³⁸); (d) autism symptoms (APSI³⁷). 2. *Parents.* (a) Correct use of *Social ABCs* strategies (%)

implementation fidelity from blind-coded video), (b) self-efficacy (Parent Self-Efficacy Scale²² developed for our previous work), (c) parenting stress (Parenting Stress Index-4-Short Form³⁹).

Exploratory Analyses:

1. **Predictor variables:** Continuous (parenting stress, child age, baseline word inventory, ASD symptoms) and categorical (toddler sex, parent gender, parenting role, educational attainment, employment, ethnicity, English spoken at home, family structure), variables (collected from the *Family Profile Form*²⁴) will be assessed for their effect on the outcomes;
2. **Implementation metrics.** We will measure *acceptability* using our post-treatment Parent Satisfaction Scale²², and a Coaches' Satisfaction Scale (under development) to capture Coaches' perceptions of the adapted model relative to the standard approach. Program *quality metrics* will include evaluation of Coaches' fidelity (based on pre-established video-coding methods). We will examine *participant flow* metrics such as referral sources, ages of children, and number referred, eligible, enrolled, and completed, as well as number of sessions attended/missed/rescheduled.
2. **Sub-group and predictor analyses** will explore child factors (e.g., age, sex, baseline language level) and family factors that are facilitators or barriers to treatment uptake and successful outcomes (e.g., parents' educational attainment, current employment, family structure, parent gender)⁴⁰, using data collected from a Family Profile Form used in our previous work²².
3. **Follow-up (treatment group only).** A 10-minute parent-child interaction video will be collected and coded for toddler responsiveness and parent implementation fidelity using the same procedures as for *time 1* and *time 2*.

2.10 Proposed sample size and justification for assumptions underlying power calculations.

We aim to enroll 120 families into the RCT, across the three participating sites.

This project has two phases, differing only by number of participants and funding source. Specifically, phase 1 (funded by Kids Brain Health Network) involves enrollment of 30 families across the 3 participating sites. For phase 2, funds are being sought through CIHR (to be adjudicated in March 2021). If funded, we will submit an amendment to increase recruitment up to 100. The proposed sample ($n = 100$; ~50 per treatment arm) will yield 80% power to detect a medium effect (at alpha = .05)⁴¹. The assumption of a medium effect comes from our previous RCT which yielded $R^2 = .43$ for the same primary outcome²². We will over-sample by 20% (i.e., recruit to $n = 120$) to allow for attrition (see 2.14). Given that this is an individually randomized group treatment trial (with 1 group-based and 1 individually administered arm) analyses will account for the intra-class correlations associated with group participation, as recommended³⁴. If Phase 2 is not funded, we will use data from Phase 1 as pilot data for further funding applications.

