2.16 What is the proposed type of analyses?

The primary analysis will yield a comparison of rates of toddler vocal responsiveness between the two conditions, controlling for the variables described above. The statistical model for the

Primary Outcome will be either a Poisson or negative binomial regression (if there is overdispersion of the counts), using the number of prompts and/or time as offsets and applying the appropriate correlation structure for observations by participant, and controlling for intraclass correlation due to clustering. Growth curve analysis will be used to calculate the trajectory of change in responsive vocalizations over time for each person based on whatever data are available (if at least 2 measurements), and then estimates (imputes) the missing data if the person followed the same trajectory. Otherwise, a worst-case (no vocal response) scenario can be used.

Secondary Outcomes: We will analyze as per the primary outcome for count variables (e.g., video-coded toddler initiations). We will use repeated measures ANOVA or Generalized Estimating Equations for scores (e.g., word inventory, ASD symptoms, parent efficacy, stress).

Exploratory Analyses: (1) *Predictors* of primary and secondary outcomes will first be assessed univariately for their effect on the outcomes, and significant factors will be subjected to multivariate analysis using the appropriate regression model. We will examine the influence of sex (toddlers), parent gender, and parenting roles by entering these factors as covariates. Given that sample size calculations are not done for all these factors, these analyses are exploratory. (2) *Implementation metrics* (feasibility, acceptability) will be examined descriptively.

[figure not shown]
2.17 Proposed frequency of analyses. Analyses will be conducted at two time points: (1) following the end of Phase 1 ($n = 30$), and (2) at the end of the larger trial ($n = 100$).

2.18 Planned subgroup analyses.

Subgroup analyses, run separately for treatment and control groups, will explore effects of: (1) sex: *Do outcomes differ for boy vs. girl toddlers?*; (2) gender: *Are there differences in parent fidelity and self-efficacy based on self-identified parent gender?*; (3) baseline language functioning: *Do outcomes differ for toddlers who begin the program below (vs. at or above) a 12-month language level (based on parent-reported CDI scores)?*

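### Three measures are both predictors and secondary outcomes, and the univariate screen does not exclude testing a measure's baseline against itself, a result that cannot show who benefits

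*Protocol*

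**What the plan says.** Section 2.8 lists among the toddler secondary outcomes "c) words understood and used, (d) autism symptoms", and lists stress among the parent outcomes. Section 2.9 names the instruments: "parent-rated word inventory (MacArthur-Bates Communicative Development Inventory" for words, "autism symptoms (APSI" for symptoms and "parenting stress (Parenting Stress Index-4-Short Form" for stress.

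The exploratory part of section 2.9 then gives the continuous predictors as "Continuous (parenting stress, child age, baseline word inventory, ASD symptoms". Three of these four are the same measures; child age is the exception. Only the word inventory is called a baseline value. Time 0 for stress and symptoms is an inference, though a natural one, because section 2.2 has questionnaires completed before allocation is revealed.

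Section 2.16 says that predictors "of primary and secondary outcomes will first be assessed univariately for their effect on the outcomes", and that significant ones go on to a multivariate model. It excludes no predictor-outcome pair. For scores, including these three, it names repeated measures ANOVA or GEE. It calls the predictor analyses exploratory.

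Section 2.9 also states an aim of finding "family factors that are facilitators or barriers to treatment uptake and successful outcomes". Section 2.18(3) compares outcomes between toddlers below and at or above a 12-month language level on baseline CDI, within each arm separately.

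**The concern.** Read literally, the screen includes stress against stress, APSI against APSI and words against words. A score taken twice on the same family a few weeks apart will be correlated with itself whether or not the program works, and whether or not some families gain more than others. A significant own-scale pair therefore carries no information about who benefits.

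What is at stake is interpretation. On score levels, high stress at entry would go with high stress later and could be read as a barrier. On change scores, the same variable could appear with the opposite sign and be read as a facilitator. Both can arise when the benefit is identical for all.

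**Working it through.** **Inputs.** From section 2.10: n = 100 (about 50 per arm) and alpha .05. From section 2.17: a further analysis at n = 30. Assumed, because the protocol does not give them: the correlation r between Time 0 and Time 1 scores among enrolled families (0.3 to 0.9), and the ratio k of the Time 1 SD to the Time 0 SD (1.0 or 1.2). Tests are two-sided at 5%.

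**The plan's own figure.** The only stated power is 80% for the primary comparison. With a medium effect taken as 0.5 SD and 50 per arm, I obtain 80.4% one-sided and 70.5% two-sided. This point does not depend on that figure; only n is reused.

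**Simulation.** 4,000 trials per setting, with the same treatment effect (0.4 SD) for every family in one arm and no differential benefit.

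**1. Time 0 against its own Time 1 score.** The correlation is r. By Fisher's z at n = 100:
- r = 0.3: 0.3095 × √97 = 3.05; 3.05 − 1.96 = 1.09, so 86% significant.
- r = 0.5: 0.5493 × √97 = 5.41; 5.41 − 1.96 = 3.45, so over 99.9%.

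Simulation agrees: 84–86% at r = 0.3 and about 100% from r = 0.5 upward. At n = 30 it gives 36%, 82% and 99% for r = 0.3, 0.5 and 0.7.

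**2. Repeated-measures model with Time 0 among the outcomes.** The between-family test compares the predictor with the family's mean score. With equal SDs and two time points, the correlation is √((1 + r)/2):
- r = 0.3: √0.65 = 0.81.
- r = 0.9: √0.95 = 0.97.

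Significance at n = 100 is practically certain. A predictor-by-time term in such a model is instead the change-score test in step 3.

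**3. Time 0 against its own change.** The correlation is (kr − 1)/√(1 + k² − 2kr), which equals −√((1 − r)/2) when k = 1. At n = 100:

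| r | k = 1.0: correlation | % significant | k = 1.2: correlation | % significant |
|---|---|---|---|---|
| 0.3 | −0.59 | 100 | −0.49 | 100 |
| 0.5 | −0.50 | 100 | −0.36 | 96 |
| 0.7 | −0.39 | 97 | −0.18 | 44 |
| 0.8 | −0.32 | 87 | −0.06 | 8 |
| 0.9 | −0.22 | 52 | +0.15 | 29 |

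The rate runs from 8% to 100%, and the sign can reverse.

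**4. Arm-by-Time 0 interaction on the same simulated data.** This is significant in 4.5% to 5.6% of trials across n = 30, 50 and 100. It keeps its nominal error rate when benefit is equal, so it addresses the question that the own-scale screen cannot.

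**5. Section 2.18(3).** Baseline CDI defines the groups. If CDI words are among the outcomes compared, the same coupling appears within each arm. With no between-arm contrast, a group difference cannot be attributed to differential benefit. I give no size here, because the share of toddlers on each side of the 12-month cut is unknown.

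**The case against.** The case against has force, and several parts of it stand.

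- **The own-scale pairing is not spelled out.** It follows from general wording, and a statistical analysis plan may exclude it. But the protocol does fix the rule (which predictors, which outcomes, tested univariately), and followed as written that rule includes these pairs.
- **The analyses are labelled exploratory.** Section 2.16 nowhere says that a significant predictor means greater benefit. The sentence on facilitators and barriers names baseline language but not stress or APSI. However, section 2.8 does list stress and ASD symptoms among the factors considered for their influence on outcomes, so the misreading is invited though not stated.
- **On score levels the association is genuine prognosis.** That is correct: it is uninformative about benefit, not false.

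A reader might infer more than the documents support:

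- **That these pairs pass at any significance level.** Not for change scores. With equal SDs, n = 100 and alpha .05/96, about 40% pass at r = 0.8 and 11% at r = 0.9. The protocol defines change only for the primary outcome.
- **That entry on APSI makes matters worse.** Section 2.5 says "Eligibility will be based on elevated scores on the Autism Parent Screen for Infants", but selecting high scores narrows the Time 0 range and weakens the correlation tested. If all were truncated at the mean with r = 0.7 and equal SDs, the Time 0 variance falls to 0.363 and the correlation with change goes from −0.39 to −0.3 × √0.363 / √(0.09 × 0.363 + 0.51) = −0.25. A confirmed diagnosis is also an entry route, so not every child is selected on APSI.
- **That taking an own baseline into the multivariate model does harm.** It does not; there it acts as ordinary adjustment. The problem is only in reporting it as a discovered predictor.
- **That the size of a spurious subgroup difference can be calculated from a median split.** Section 2.18(3) uses a 12-month language level, not the median.

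**Conclusion.** The point holds in a limited form and is minor. Three of the four continuous predictors are also secondary outcomes, and nothing in sections 2.9 or 2.16 keeps a measure from being screened against itself. For score-level analyses, and for the between-family test of a repeated-measures model, significance at n = 100 is close to certain with equal benefit for all. This rests on the assumed correlation (0.3 or more, effectively certain from 0.5 for the Time 1 score) and on Time 0 being meant for stress and symptoms. For change scores no general statement is possible without the correlation and SD ratio.

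The same measures tested against the primary outcome or against other secondary outcomes are not affected. The primary analysis, the sample size and the confirmatory conclusions are untouched.

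**What to change.** In sections 2.9 and 2.16:
- State that parenting stress, word inventory and ASD symptoms are taken at Time 0 when used as predictors.
- State that a measure is not reported as a predictor of itself, and that each outcome's own Time 0 value enters its model only as an adjustment covariate.
- Where the question is whether benefit depends on starting level, report the arm-by-Time 0 interaction with its confidence interval.

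In section 2.18(3), report the arm-by-subgroup interaction in place of a reading of each arm alone, at least where CDI words are the outcome.

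The cost is a few sentences: no new data and no change to the sample size. The interaction will be estimated imprecisely with about 50 families per arm, which suits its exploratory status.
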